### 1.1 Study design

This is a Phase II, multicenter, randomized (1:1), open-label study to compare the efficacy and safety of eltrombopag in combination with a short course of high-dose dexamethasone to 1-3 cycles of high-dose dexamethasone monotherapy, as first-line treatment in adult patients with newly diagnosed immune thrombocytopenia (ITP).

Randomization to treatment will follow a 1:1 ratio. No stratification is applied. A total of n=106 will be enrolled.

No interim analysis is planned. The analysis will be performed once all patients completed their final visits or terminated the study prematurely.

Objectives		Endpoints		
Primary Objective		Endpoint for primary objective		
1.	To compare the ability of eltrombopag in combination with a short course of dexamethasone to induce a sustained response off treatment at 52 weeks versus a defined course of dexamethasone	
 
Rates of patients achieving a sustained response off treatment at 52 weeks, comparing the two arms         (sustained response off treatment = maintain platelet count ≥ 30 × 10^9/L after treatment discontinuation in the absence of bleeding events ≥ Grade II or use of any rescue medication at all visits until Week 52)
 
		
Se	econdary Objectives	Endpoints for secondary objectives		
1.	To compare the ability of eltrombopag in combination with a short course of dexamethasone to induce overall response (OR) after treatment discontinuation at Week 52 versus a defined course of dexamethasone	
 
Proportion of patients with platelet count         ≥ 30 × 10^9/L and ≥ 2-fold increase of screening         platelets after treatment discontinuation in the         absence of bleeding events ≥ Grade II and no         rescue therapy at all visits until Week 52     
 
		
2.	To assess the duration of sustained response off treatment	
 
Median duration of sustained response off treatment calculated from the time of treatment discontinuation until platelet count < 30 × 10^9/L or bleeding events ≥ Grade II or use of any rescue therapy
 
		
3.	To assess the ability of eltrombopag to induce overall response (OR) by Week 4	
 
Proportion of patients with platelet count         ≥ 30 × 10^9/L and ≥ 2-fold increase of screening         platelet count and absence of bleeding and no         rescue therapy at least once by Week 4     
 
		

#### 1.2 Study objectives and endpoints

Objectives		Endpoints		
4.	To assess the ability of eltrombopag to induce complete response (CR) by Week 4	٠	Proportion of patients with platelet count $\geq 100 \times 10^{9}$ /L and absence of bleeding and no rescue therapy at least once by Week 4	
5.	To quantify the increase in platelet count from baseline to 1, 2, 4, 12, 26, and 52 weeks	•	Absolute values and relative changes in platelet count from screening to 1, 2, 4, 12, 26, and 52 weeks	
6.	To assess the time to overall and complete response	•	Time from starting treatment to time of achievement of overall and complete response	
7.	To assess the duration of overall and complete response		Duration of overall and complete response as defined above	
8.	To evaluate patient-oriented outcomes for health-related quality of life	•	The analysis of Health–Related Quality of Life (HRQoL) parameters by use of Functional Assessment of Chronic Illness Therapy (FACIT) and Short Form 36 version 2 (SF36v2) questionnaires. Change in scores from baseline to 1, 2, 4, 12, 26 and 52 weeks	
9.	To evaluate the safety and tolerability of eltrombopag + dexamethasone	•	Changes from baseline in physical exam findings, clinical monitoring, vital signs, clinical laboratory tests, and evaluation of reported adverse events	
10.	To evaluate the incidence and severity of bleeding events	•	Incidence and severity of bleeding assessed by the World Health Organization (WHO) Bleeding Scale	
		I		

# 2 Statistical methods

#### 2.1 Data analysis general information

Data analysis will be performed by the CRO version 9.4 or higher is used.

. The software SAS,

The statistical analysis will be based on all subject data at the time the trial ends. This analysis will be performed once all patients completed their final visits or terminated the study prematurely.

Continuous variables will be summarized by number of patients, mean, standard deviation, minimum, median, and maximum. For selected parameters, 25th and 75th percentiles will also be presented. Categorical variables will be summarized by frequencies and percentages. The 95% confidence interval (CI) using the Clopper-Pearson method will be provided for selected parameters. Kaplan-Meier method will be used for time to event analyses.

### 2.1.1 General definitions

**Study treatment** for patients randomized to the investigational combination treatment is eltrombopag until Week 26 in combination with 1 cycle of high-dose dexamethasone (subsequently referred to as treatment group ETB+DEX). For patients randomized to the control arm the study treatment consists of 1-3 cycles of high-dose dexamethasone (subsequently

referred to as treatment group DEX). These treatments will be called "study treatment" in the rest of the document.

When eltrombopag and/or dexame thas one will be given additionally, this is assessed as rescue or - if applicable - as concomitant medication during the data review meeting case-by-case.

The last available assessment on or before the date of start of eltrombopag is taken as "**baseline**" assessment. It is assumed that all assessments at Week 1/Day 1 are captured pre-dose on first day of eltrombopag (e.g. PROs), thus this Week 1/Day 1 is used for baseline when no screening values are available. Otherwise the screening values are considered as baseline. For all analyses on platelets the platelet count directly before pre-treatment will be used as baseline value in the pretreated patients. This is the more adequate way of taking into account the initial value at time of diagnosis and before pre-treatment for all patients

**Pre-treatment period**: from day of subject's informed consent to the day before first dose of study treatment.

**On-treatment period**: from date of first dose of study treatment to date of treatment discontinuation (including start and stop date).

**Treatment discontinuation** is the date of last study medication given as study treatment but not as rescue medication or not after after re-initiation, i.e. initial dose after failure of 1-3 DEX cycles (for details see Derivation of time point of treatment discontinuation5.1).

**Post-treatment period**: starting at day 30+1 after last dose of study treatment

The **Safety Follow-up period** specifies the observational period (30d) for which patients will be followed-up for safety events/measures.

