- Screening Period: Patients will be screened based on the inclusion and exclusion criteria specified in Section 5.1 and Section 5.2, respectively.
- Treatment Period:

Arm A: Patients will be treated for 26 weeks (6 months) during the treatment period. Patients who reach platelet counts $\geq 30 \times 10^{9}/L$ and maintain counts $\geq 30 \times 10^{9}/L$ during the tapering phase will be eligible for treatment discontinuation. Duration of tapering before treatment discontinuation at Week 26 will be 6 weeks.

Arm B. Patients will be treated up to 12 weeks (3 months) during the treatment period. Patients who reach platelet counts $\geq 30 \times 10^9$ /L and maintain counts $\geq 30 \times 10^9$ /L after 1-3 cycles of dexamethasone treatment will be eligible for treatment discontinuation. Patients with platelet counts $< 30 \times 10^9$ /L after 3 cycles of dexamethasone treatment will be offered a course of eltrombopag treatment within the study and will discontinue from study at Week 52.

• Observation period: After completion of treatment period, patients will be observed for sustained response off treatment.

Arm A: Patients who successfully taper off, discontinue eltrombopag and maintain platelet counts $\geq 30 \times 10^{9}$ /L in the absence of bleeding or use of any rescue therapy will be observed until Week 52 after study start. Patients who relapse after eltrombopag discontinuation will reinitiate treatment with eltrombopag till Week 52 and will discontinue from study at Week 52. Patients with platelet counts $< 30 \times 10^{9}$ /L after 26 weeks of treatment with eltrombopag will continue eltrombopag treatment till Week 52 and discontinue from study at Week 52.

Arm B: Patients who successfully discontinue dexamethasone treatment and maintain platelet counts $\geq 30 \times 10^{9}$ /L in the absence of bleeding or use of any rescue therapy will be observed until Week 52 after study start. Patients who relapse (platelet count < 30 × 10⁹/L) after dexamethasone discontinuation and need treatment will be treated with eltrombopag until Week 52 after study start and discontinue from study at Week 52. Patients with platelet count < 30 × 10⁹/L after 3 cycles with dexamethasone will initiate treatment with eltrombopag and discontinue the study at Week 52.

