The **baseline** is the result of an investigation describing the state of the patient before start of eltrombopag or dexamethasone study treatment, and after a possible pre-treatment. The screening value describes the result at screening, before pre-treatment, especially for the thrombocyte count (see exclusion criteria). Should a patient not need pre-treatment, Screening

and baseline values can be identical. In such cases, as only one assessment exists, the baseline value will be taken from screening.

The last available assessment on or before the date of start of eltrombopag / dexamethasone study treatment is taken as "baseline" assessment. In case, assessment is captured pre-dose on first day of study treatment (e.g. PROs), this assessment is used for baseline.

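### SAP 2.1.1 contradicts both itself and the protocol on baseline: it anchors baseline to eltrombopag alone and ranks screening values above Day 1 values, with no departure declared

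*SAP*

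**What the plan says.** The protocol defines baseline twice, consistently. Its glossary takes the last assessment available up to the start of study treatment. Section 12 names both drugs: "The last available assessment on or before the date of start of eltrombopag / dexamethasone study treatment is taken as" baseline. It adds that baseline describes the patient after any pre-treatment, whereas the screening value describes the patient before it. Section 12 takes baseline from screening only where a patient was not pre-treated and has a single assessment.

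SAP section 2.1.1 is worded differently. It opens with "The last available assessment on or before the date of start of eltrombopag is taken as" baseline. It continues: "It is assumed that all assessments at Week 1/Day 1 are captured pre-dose on first day of eltrombopag", and concludes "thus this Week 1/Day 1 is used for baseline when no screening values are available". The next sentence reads "Otherwise the screening values are considered as baseline". Platelets have a rule of their own: "For all analyses on platelets the platelet count directly before pre-treatment will be used as baseline value in the pretreated patients". The same section describes Arm B: "For patients randomized to the control arm the study treatment consists of 1-3 cycles of high-dose dexamethasone".

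SAP section 2.8.3 uses this baseline for laboratory changes (to the last on-treatment value) and for shift tables (to the worst on-treatment value). SAP section 4 reports no change from the protocol's analyses.

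**The concern.** The SAP departs from the protocol in two ways, and its sentences do not agree with each other. Anchoring baseline to the start of eltrombopag leaves out dexamethasone, which is the only study treatment in Arm B. Ranking screening above Day 1 reverses the last-available principle stated just before it: where both values exist, the later one is Day 1.

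The safety tables are at stake. A change or shift should be measured from the patient's state immediately before study drug. If the reference value was drawn before a short course of ITP-directed pre-therapy, any effect of that course on laboratory values is counted as an on-study change. Since Amendment 3 all analyses are descriptive, so these tables are themselves the result, and no model adjusts for a misplaced reference value. Because SAP section 4 declares no change, a reader of the report would assume that the protocol's baseline had been used.

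**Working it through.** The plan states no figure that depends on the baseline definition, so the check sets the texts side by side and applies the rules case by case.

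**Inputs**
- Baseline rules: protocol glossary and section 12; SAP 2.1.1.
- Screening takes place 1 to 14 days before randomization (protocol 8.1), and randomization is at Week 1 Day 1 (protocol 6.1.3).
- Pre-therapy is allowed for at most 3 days within the 7 days before randomization (protocol 5.2, exclusion 1).
- Hematology, chemistry and vital signs are scheduled at both screening and Day 1. FACIT-Fatigue and SF-36v2 are scheduled at Day 1 and not at screening (protocol Table 8-1).

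**Which value each rule selects**
1. *Either arm, both values present.* The protocol selects Day 1. The first SAP sentence, applied to Arm A, also selects Day 1. The later SAP sentences select screening. The SAP therefore gives two answers for the ordinary case.
2. *Arm B, eltrombopag never given.* The first SAP sentence supplies no anchor date. The later sentences supply screening, or Day 1 if screening is missing.
3. *Arm B, eltrombopag given later.* Protocol section 3 says that patients with low counts "after 3 cycles with dexamethasone will initiate treatment with eltrombopag and discontinue the study at Week 52". The first SAP sentence, taken literally, would select a value after dexamethasone. The later sentences select screening.
4. *FACIT-Fatigue and SF-36v2.* There is no screening value, so Day 1 is used under both documents.

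**When pre-therapy effects enter laboratory changes under the screening rule**
- A screening sample drawn 8 to 14 days before randomization precedes any permitted pre-therapy, because that therapy lies within the last 7 days.
- A sample drawn 1 to 7 days before randomization may come before, during or after pre-therapy.
- The effect enters only if the patient was pre-treated and the sample was drawn before pre-therapy had acted. In patients without pre-treatment it does not arise.
- The documents give neither the number of pre-treated patients nor the order of sampling, so no size can be calculated.

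**Platelets**
- Protocol Table 2-1 (objective 5) and section 12.5.1 (item 6) plan the platelet change from screening to baseline and then to later weeks.
- Under SAP 2.1.1, baseline equals the count before pre-treatment in pre-treated patients and the screening count in the others. Screening minus screening is zero, so the change has no content. SAP 2.7.1 (item 5) no longer lists it.
- The primary logistic model names the screening count explicitly, defined as the count before pre-treatment where there was any (SAP 2.5.2). The overall-response definitions also refer to screening. Neither depends on the baseline rule.

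**Internal check**
SAP 2.8.1 and 2.8.3 start the on-treatment period at the first dose of eltrombopag or dexamethasone, whichever comes first. That anchor covers both arms and matches the protocol, whereas the baseline anchor does not.

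**The case against.** The best defence is that the eltrombopag anchor is a drafting omission. The on-treatment definition names both drugs, and the sentence equating Day 1 with the first day of eltrombopag shows that study entry was meant. The screening sentence has no arm restriction, so every patient receives a pre-dose value. The pre-treatment platelet reference is a reasoned choice that follows Amendment 2. The protocol itself accepts a screening value as baseline in one situation, and the analyses are descriptive in about 24 patients.

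Much of this stands, and it rules out three stronger conclusions that a reader might draw.

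- *Arm B has no valid baseline.* This follows only if the first sentence is read alone. The later sentences give Arm B screening, or Day 1 if screening is missing.
- *Baseline in crossover patients falls about two months after first dose.* This belongs to the eltrombopag-anchor reading, which the screening sentence displaces; the two harms cannot both occur in the same patient. The timing is not fixed either. With 28-day intervals the third four-day cycle ends on day 1 + 2×28 + 3 = 60. With the permitted 14-day intervals it ends on day 1 + 2×14 + 3 = 32. Neither day is an assessment date.
- *Safety changes are not comparable between arms.* The screening rule is the same in both arms and pre-therapy precedes randomization, so its effect is balanced in expectation. The reference point moves for some patients, but no systematic between-arm bias follows.

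The defence does not explain the preference for screening over Day 1. That is an explicit rule, contrary to the protocol wherever Day 1 values exist, and it is not declared.

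**Conclusion.** The point holds as an inconsistency that should be corrected. SAP 2.1.1 contradicts itself, uses an anchor that does not apply to Arm B at entry, and, followed as written, sets aside the Day 1 hematology and chemistry values that the protocol treats as baseline.

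The consequences are limited. The reference value for laboratory changes and shift tables may be 1 to 14 days older than Day 1. Pre-therapy effects enter only for pre-treated patients whose screening samples came first, and how many there are is unknown. The protocol's screening-to-baseline platelet change is lost. For vital signs the reach is less clear: SAP 1.2 lists change from baseline as an endpoint, but SAP 2.8.4.3 plans only summaries by visit.

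This rests on two assumptions: that the screening sentence is the operative rule when both values exist, and that Day 1 samples were taken before dosing, as the SAP itself assumes.

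**What to change.** In SAP 2.1.1, replace the baseline definition with the last non-missing assessment on or before the first dose of eltrombopag or dexamethasone, whichever is first. This is normally the Day 1 pre-dose value, with screening used only if Day 1 is missing. Keep the platelet count before pre-treatment as a separately named screening value for the primary model and the response definitions, and do not call it baseline. Restore the screening-to-baseline platelet change in SAP 2.7.1 (item 5). List any departure that remains in SAP section 4.

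The cost is SAP wording and one change to the derivation program; the Day 1 data are already scheduled. If the tables have been produced, a short addendum and a rerun of the change and shift tables are also needed.

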#### 2.2 Analysis sets

The Full Analysis Set (FAS) will consist of all patients to whom study treatment has been assigned by randomization. The FAS will serve as the primary analysis set for all efficacy analyses. According to the intent to treat principle, subjects will be analyzed according to the treatment they have been assigned to during the randomization procedure.

Before database lock, relevant protocol deviations and potential impact on analyses will be reviewed and adequately processed / documented.

The Safety Set (SAF) includes all subjects who received at least one dose of study treatment. Subjects in the SAF will be analyzed according to the study treatment actually received. During the Data Review Meeting the study treatment actually received will be assessed.

#### 2.2.1 Subgroup of interest and relevant cofactor

The primary endpoint and related parameters will be displayed for the following subgroups:

• Age ( $\leq$  vs. > 60 years)

- Platelet count: thrombocytopenia at screening respectively before pre-treatment (<10 x 10^9/L versus ≥10 x 10^9/L)
- ITP-directed pre-therapy (yes/no)

# 2.3 Patient disposition, demographics and other baseline characteristics

Demographic and other baseline data including disease characteristics will be listed and summarized descriptively by treatment group and overall for the FAS.

Relevant medical histories and current medical conditions at baseline will be summarized separately by system organ class and preferred term, by treatment group and overall.

#### 2.3.1 Patient disposition

Patient disposition displays the absolute and relative frequency of screening failures, randomized patients (i.e. FAS), randomized and treated patients (=SAF), and patients completed Week 53. The frequency of reasons for permanent discontinuation of study treatment, and reasons for study discontinuation before Week 53 will be presented.

# 2.4 Treatments (study treatment, rescue medication, concomitant therapies, compliance)

#### 2.4.1 Study treatment / compliance

The Safety set (SAF) will be used for the analyses below. If FAS and SAF are not identical the analyses will be repeated for the FAS.

The duration of exposure in weeks to study treatment eltrombopag and dexamethasone as well as the dose intensity (computed as the ratio of actual cumulative dose received and actual duration of exposure) and the relative dose intensity (computed as the ratio of dose intensity and planned dose intensity, and shown separately as well as combined for both drugs) will be summarized by means of descriptive statistics.

The mean dose will be calculated for the on-treatment period and displayed by summary statistics.

For patients who need treatment after Week 27 resp. Week 13 the mean dose until their last intake of the medication is displayed by summary statistics.

The number of subjects with dose adjustments (reductions, interruption, or permanent discontinuation) until Week 53 and the respective reasons will be summarized by treatment group and all dosing data will be listed.

A cross table displays the frequency of patients who are eligible / non-eligible for treatment discontinuation versus real treatment discontinuation (no/yes at that time point).

<sup>1 For patients who were pre-treated with ITP-directed therapies the last platelet count before start of pre-

treatment is used. For patients who were not pretreated the platelet count at screening.

<sup>2 averaged

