Patients who relapse (< 30×10 ⁹ /L) after eltrombopag discontinuation before Week 52	Re-initiate treatment with eltrombopag with a starting dose of 50 mg/day till Week 52 and discontinue from study at Week 52	

Treatment in the control arm consists of 1-3 cycles of high-dose dexamethasone administered orally at a dose of 40 mg QD for 4 consecutive days at 4 weeks intervals (dexamethasone can also be given at 14 to 28 days intervals if needed according to current ITP guidelines). If the platelet counts are $> 150 \times 10^{9}$ /L no further course of dexamethasone will be given. Patients will be treated up to 12 weeks (3 months) during the treatment period with dexamethasone. Patients who reach platelet counts $\ge 30 \times 10^{9}$ /L and maintain counts $\ge 30 \times 10^{9}$ /L after 1-3 cycles of high-dose dexamethasone treatment will be eligible for treatment discontinuation. Patients with platelet counts $< 30 \times 10^{9}$ /L after 3 cycles of dexamethasone treatment will be offered a course of eltrombopag treatment within the study and will discontinue the study after completion of treatment with eltrombopag at Week 52 (Table 6-2).

Table 6-2Dexamethasone dosing guidance for patients not meeting criteria for
sustained remission

Platelet Level	Dose Guidance
Patients with platelet count < 30×10 ⁹ /L after 3 cycles with dexamethasone	Initiate treatment with eltrombopag with a starting dose of 50 mg/day and continue treatment with eltrombopag till Week 52 after study start and discontinue from study at Week 52
Patients who relapse (platelet count < 30×10 ⁹ /L) after dexamethasone discontinuation before Week 52	Initiate treatment with eltrombopag with a starting dose of 50 mg/day till Week 52 after study start and discontinue from study at Week 52

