12.3 Treatments

The Safety set will be used for the analyses below.

The duration of exposure in weeks to eltrombopag and dexamethasone as well as the dose intensity (computed as the ratio of actual cumulative dose received and actual duration of exposure) and the relative dose intensity (computed as the ratio of dose intensity and planned dose intensity, and shown separately as well as combined for both drugs) will be summarized by means of descriptive statistics using the safety set.

The number of subjects with dose adjustments (reductions, interruption, or permanent discontinuation) and the respective reasons will be summarized by treatment group and all dosing data will be listed.

Furthermore, subjects using rescue treatments as defined in Section 6.2.3 will be summarized by treatment group.

Concomitant medications and significant non-drug therapies prior to and after the start of the study treatment will be listed and summarized according to the Anatomical Therapeutic Chemical (ATC) classification system, by treatment group.

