# 5 Appendix

### 5.1 Derivation of time point of treatment discontinuation

The time point of **treatment discontinuation** is the date of last dose of study medication given as study treatment but not as rescue medication, not after re-initiation or not after as initial dose after failure of 1-3 DEx cycles, and not as concomitant medication (if applicable).

For patients randomized to DEX monotherapy the time point of treatment discontinuation is the date of last study medication dexamethasone documented on the "End of Treatment" CRF. During the data review meeting it will be verified, that this date corresponds to the stop of study treatment but not to the stop of rescue medication.

For patients randomized to ETX+DEX combination therapy the time point of treatment discontinuation is the maximum date of the study medications eltrombopag and dexamethasone documented on the "End of Treatment" CRF, in general. When the primary reason for permanent discontinuation of eltrombopag is:

- "stop of eltrombopag re-initiated after relapse", or
- "stop of eltrombopag as rescue medication for patients randomized to DEX monotherapy" or
- the free text specification of "other reason" indicate that elthombopag was re-initiated or used after switch from DEX to ETB

the stop of study treatment eltrombopag has to be visually assessed from the data of the "Eltrombopag – Dosage Administration Form" during the data review meeting.

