#### 5.1.1 Derivation of exposure to study treatment

Exposure to study treatment is calculated by:

```
Date of treatment discontinuation – date of first dose + 1 day
```

It should be mentioned, that interruptions, i.e. when study treatment is restarted, are included in the exposure to study treatment.

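### Dexamethasone dose intensity in Arm B falls as cycles are added at any fixed interval, and the SAP defines neither per-drug exposure nor the planned intensity for the flexible regimens

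*SAP*

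**What the plan says.** SAP 2.4.1, following protocol 12.3, plans descriptive statistics for the duration of exposure to each drug and for "dose intensity (computed as the ratio of actual cumulative dose received and actual duration of exposure". Protocol 12.3 adds "the relative dose intensity (computed as the ratio of dose intensity and planned dose intensity, and shown separately as well as combined for both drugs"; a footnote in SAP 2.4.1 explains that combined means averaged.

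The only derivation of exposure is in SAP 5.1.1: "Date of treatment discontinuation – date of first dose + 1 day". The same section states that "interruptions, i.e. when study treatment is restarted, are included in the exposure to study treatment".

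The end date comes from SAP 5.1, one per patient. In Arm B it is "the date of last study medication dexamethasone documented on the" End of Treatment form. In Arm A it is, in general, "the maximum date of the study medications eltrombopag and dexamethasone documented on the" same form.

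Arm B dexamethasone is "administered orally at a dose of 40 mg QD for 4 consecutive days at 4 weeks intervals" (protocol 6.1), for one to three cycles. Intervals of 14 to 28 days are also permitted, and no further course is given above a platelet count of 150 × 10⁹/L. Arm A receives one such four-day cycle plus eltrombopag for 26 weeks. Eltrombopag is titrated to platelet count and then tapered. Neither document gives a numerical planned dose intensity.

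**The concern.** Dose per unit of calendar time suits a drug taken every day. For a pulsed drug, the span from first to last dose includes the drug-free gaps between cycles and leaves out the one after the last cycle. A one-cycle patient has no gap in the denominator; a three-cycle patient has two. The summary can therefore rank the patient with the least steroid as the most intensively treated.

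Two further gaps matter. One discontinuation date per patient leaves it open which dates apply to dexamethasone in Arm A. And a relative intensity needs a planned value, which is not stated for the regimens that vary by design.

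Steroid exposure is worth describing well here. Protocol 1.1.1 gives less long-term corticosteroid use as part of the background, and protocol 4.3 limits Arm A to one cycle for tolerability. After Amendment 3 about 24 patients are expected and all analyses are descriptive, so exposure tables form part of the context for reading safety by arm. SAP 2.4.1 names no summary of the number of cycles or of cumulative dexamethasone dose.

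**Working it through.** The documents state no dose-intensity value, so there is no figure to reproduce.

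**Inputs**
- Dose per cycle: 40 mg × 4 days = 160 mg (protocol 6.1).
- Cycles in Arm B, *c*: 1 to 3. Interval, *g*: 28 days as standard, 14 to 28 permitted (protocol 6.1). I take *g* from the start of one cycle to the start of the next and assume full dosing.
- Duration: last date − first date + 1, gaps included (SAP 5.1.1).
- Arm A: one cycle, 160 mg; eltrombopag for 26 weeks × 7 = 182 days (protocol 6.1.4).

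**Arm B**

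Span = *g*(*c* − 1) + 4 days. Dose intensity = 160*c* / span.

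| Interval | 1 cycle (160 mg) | 2 cycles (320 mg) | 3 cycles (480 mg) |
|---|---|---|---|
| 28 d | 160/4 = 40 | 320/32 = 10 | 480/60 = 8 |
| 21 d | 160/4 = 40 | 320/25 = 12.8 | 480/46 = 10.4 |
| 14 d | 160/4 = 40 | 320/18 = 17.8 | 480/32 = 15 |

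All values are mg/day. The formula can be rewritten as 160 / (*g* − (*g* − 4)/*c*). For any *g* above 4 the denominator grows with *c*, so intensity falls with each added cycle at every permitted interval. The largest value for more than one cycle is 17.8, so a one-cycle patient always ranks first. From one to three cycles the dose triples while intensity falls 40/8 = 5-fold at 28 days, or 40/15 = 2.7-fold at 14 days. If the 28 days run from the end of one cycle to the start of the next, three cycles give 480/68 = 7.1.

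The cause is the uncounted last gap. Dividing by dosing days gives 40 mg/day for any number of cycles. Dividing by full cycle lengths gives 160/28 = 5.71 or 160/14 = 11.43 mg/day for any number. Either denominator removes the fall.

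**Arm A**
- Dexamethasone over its own dates: 160/4 = 40 mg/day.
- Dexamethasone over the combination-level span: 160/182 = 0.88 mg/day.
- Ratio for the same 160 mg: 182/4 = 45.5.

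**Relative dose intensity in Arm B**

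The planned value is not given, so two assumed values show the range, using 28-day cycles.
- Planned = 8 mg/day (three cycles): a correctly treated one-cycle patient scores 40/8 = 500%.
- Planned = 40 mg/day (one cycle): a fully compliant three-cycle patient scores 8/40 = 20%.

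**The case against.** The strongest reply is that this is one descriptive summary among several. SAP 2.4.1 also plans duration of exposure, mean dose, dose adjustments with reasons, and a listing of all dosing data. With about 24 patients the listing lets a reader see each course directly. Compliance is assessed separately by pill count (protocol 6.6.1). No efficacy endpoint or decision rule uses dose intensity. All of this stands and limits the importance of the point, but it does not make the summary right.

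Four stronger readings are tempting, and the documents do not support them:
- *Steroid exposure is ranked backwards throughout Arm B.* It is not. Three cycles at 14 days (480 mg) give 15 mg/day, against 10 for two cycles at 28 days (320 mg), so there the order is correct. The fall holds at a fixed interval, and a one-cycle patient always comes first.
- *Arm A dexamethasone will be reported as 0.88 mg/day.* That follows only if the combination-level date is applied to dexamethasone. SAP 2.4.1 names both drugs and asks for separate display, and SAP 5.1 draws on an end date for each drug, so per-drug spans may be intended. What is missing is a written rule.
- *A one-cycle patient will show 500%.* That rests on a planned value which no section states. A planned value matched to the cycles given would return 100% for a compliant patient.
- *No planned intensity exists for any component.* Dexamethasone in Arm A has a fixed plan: one cycle of 160 mg over four days. The gap concerns the one-to-three-cycle regimen and titrated eltrombopag.

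**Conclusion.** The point holds for Arm B on the written rules alone: SAP 2.4.1 and 5.1.1 together produce a dexamethasone intensity that falls with cycle number at any fixed permitted interval. From one to three cycles it goes from 40 to 8 mg/day at 28 days, or from 40 to 15 at 14 days, while cumulative dose goes from 160 to 480 mg. These sizes assume full dosing and start-to-start intervals; the direction is the same at every permitted interval.

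The Arm A difference, 0.88 against 40 mg/day, is an ambiguity between two readings and not a settled result. Relative dose intensity for the one-to-three-cycle regimen and for eltrombopag lacks a stated reference. Its average over the two drugs inherits that defect and is not interpretable.

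The consequence is confined to the exposure summaries. It is worth correcting because the rule as stated gives a misleading ordering and the remedy is cheap.

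**What to change.** In SAP 2.4.1 and 5.1.1:
- Derive exposure per drug, from that drug's own first and last dates as randomised study treatment. Keep the combination-level date in SAP 5.1 for defining treatment discontinuation.
- For dexamethasone, replace dose intensity with number of cycles, dosing days, cumulative mg, and mg taken / (160 mg × cycles started). The last ratio will sit near 100% for most patients and only checks completion within cycles; cycles and cumulative mg carry the information.
- For eltrombopag, report mean daily dose over its own span, with zero-dose days shown separately.
- Delete the averaged relative dose intensity.
- Record the departure from protocol 12.3 in SAP section 4, which now states that there is none.

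The inputs come from the dosage administration records for both drugs named in SAP 5.5.1. I do not suggest a ratio to prescribed mg, because the documents do not show that prescribed mg is held in the eCRF.

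The cost is SAP wording, minor reprogramming of one descriptive table and a stated departure from the protocol. The SAP history says version 3.0 was agreed before database lock and signed shortly after, so this would be a late change and should be documented as such.
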